the subarachnoid space can allow CSF to bypass an obstruction, thus obviating the need for a VP shunt. The use of endoscopic third ventriculostomy (ETV) is now becoming more prevalent in the primary treatment of hydrocephalus particularly in cases of obstruction and a consensus of opinion exists regarding their high likelihood of success in these cases¹³. The use of ETV is also gaining popularity in the treatment of shunt malfunction even in cases where there was a communicating hydrocephalus to begin with. There are several papers advocating this (secondary ETV) as a worthwhile alternative to shunt revision. In some cases particularly in older patients ETV has been suggested as a treatment for shunt blockage in patients whose hydrocephalus was originally communicating^{3,5,7,9,20,25}.

In this unit we perform approximately 100 shunt revisions per year. In 2004, we performed 108 shunt revisions. In 47 of those cases (43.5%), a further procedure was needed because of complications with the new shunt. The 1-year survival revised shunts in 2004 was therefore 56.5%. There are series which show higher success rates (70%) with ETV following shunt failure²⁰. These are retrospective.

To date there has been no prospective analysis comparing ETV to shunt revision in patients who present with shunt problems requiring surgery.

Study objective:

The aim of this study is to compare the success rates of ETV and shunt revision in the treatment of shunt malfunction in patients with hydrocephalus, In other words to:

- determine which group of patients are most likely to require further surgery within a one year follow-up period
- To compare immediate complication rates between the two patient groups

Sample population:

All patients presenting to Leeds General Infirmary with shunt obstruction will be considered for the study regardless of the original cause of their hydrocephalus.

Inclusion criteria:

1. Symptoms/signs or radiological evidence of shunt obstruction
2. Ventricular anatomy making an endoscopic procedure feasible as judged by the attending consultant neurosurgeon:
 - a. Lateral and third ventricles adequate size
 - b. Thin third ventricle floor
 - c. Adequate pre-pontine cistern to fenestrate into with an endoscope
3. Age greater than one year

Exclusion criteria

1. Age less than one year (these children are less likely to benefit from ETV^{2,6,14-16,18,23,24})
2. Small ventricles preventing passage of the endoscope

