Those that are randomised to shunt revision will have part or all of the shunt replaced. Patients randomised to the ETV arm of the study may have the malfunctioning shunt left in situ. Once the patient has had their surgery, they will be kept in hospital until they are deemed well enough for discharge home. There will be a visual assessment prior to discharge.

Follow-up will be arranged for 6 weeks, 6 months and one year for all study patients. At the 6 week and 6 month clinic the patient will have a cranial imaging to assess ventricular size. Those that have had an ETV will have an MRI scan to determine patency of the stoma as well (this is normal practice

following such a procedure). If a shunt revision is performed, a CT or MRI will be performed. Fundoscopy and visual acuity are also assessed in clinic. This is no different from the normal follow-up of a patient who has had treatment of a blocked shunt.

Should a patient make an unscheduled presentation because of symptoms related to their hydrocephalus or surgery and recurrence of the hydrocephalus is suspected they will be investigated in the usual manner in such cases (i.e. clinical and/or radiological confirmation of failure of shunt or ETV if that is the case).

A final proforma will be filled in at the patient's exit from the study. Exit from the study can happen in 3 ways:

- The patient represents with shunt/ETV failure
- The patient is well at one year following surgery with no need for further surgical intervention
- The patient voluntarily withdraws from the study for any reason at all

Duration of the study

Subject to R&D and ethics committee approval, enrolment into the study will commence on January 1st, 2007 and we would expect to enrol the 200th patient by December 31st, 2010. To ensure a minimum of one years-follow-up, data accrual will continue for one year after recruitment of the 200th patient. Overall we would expect this study to last at most 5 years.

Treatment efficacy assessment/endpoints:

In each patient the following endpoints will be assessed:

Primary endpoint:

One-year success rate of the procedure (one-year survival of shunt or ETV)

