Obviously, a patient or family can withdraw from the study at any point. If they withdraw at any point before the one-year follow-up, they will be excluded from analysis at the end of the study.

Is endoscopic third ventriculostomy an effective treatment in patients with hydrocephalus and cerebrospinal fluid shunt malfunction?

Data recording and proformas

All data will be recorded prospectively on proformas by one of the investigators:

There will be a proforma for

- The initial inpatient admission, surgery and discharge
- Follow-up proforma to be filled in at one year or earlier if treatment fails

Data storage:

All proformas will be kept in paper form by the principle investigator in his office and will be transferred onto a computer database on one desktop PC in the department of neurosurgery. This will be password controlled and only the named investigators will have access to it

ETV vs. Shunt Revision Study: admission

Hospital number 1

Surname First name Date of birth Date of entry into study

Admission details

Date of admission
 
Mode of presentation
 
 Self referral
 
 Through OPD
 
 GP
 
 Other hospital
 
 A&E
 
 Other...
	
Cause of hydrocephalus
 
 IVH
 
 Aqueduct stenosis
 
 Myelomeningocele
 
 Chiari malformation
 
 Tumour
 
 CSF infection
 
 Head injury
 
 Dandy Walker
 
 Craniosynostosis
 
 Venous thrombosis
 
 Unknown
 
 Other

---	---

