- ventricle size decreased (still large)
- ventricle size unchanged (normal)
- ventricle size unchanged (still large)
- ventricle size increased
- Other...

MRI

- not done
- ventricle size decreased (normal)
- ventricle size decreased (still large)
- ventricle size unchanged (normal)
- ventricle size unchanged (still large)
- ventricle size increased
- flow through stoma (if ETV)
- Other...

Number of visits post discharge

Complications post-op	Free text
-----------------------	-----------

Status

- Functioning at one year
- Failed before one year
- Dead
- Lost to follow-up

Symptoms in successful patients

- none
- mild
- severe (requiring admissions)

Where failed: Date of failure

- Operation for failure
- shunt
 - ETV again
 - Other...

Cause of failure Free text

Statistical considerations:

The primary endpoints will be compared by a chi-squared test comparing success rates at one year in each group.

The timing of failure in those treatments that do fail will be compared using the Kaplan-Meier survival curves.

Complication rates are expected to be small and we expect no statistical difference in a study this size.

Mean numbers of reattendances and mean reduction in ventricular size will be compared using student's t-test

Data storage

All data will be stored on a PC and in paper form in the neurosurgical department.

Patients will be identified by their hospital numbers and only neurosurgical medical staff will have access to the data

Ethical considerations

There are no specific ethical issues in this study. Both treatments are well-recognised alternatives for managing patients with hydrocephalus

Publication of study findings

We plan to publish the results of this study in Journal of Neurosurgery

Presentations of the data will be made to at academic meetings (e.g. European Society for Pediatric neurosurgery and/or the International Society for Pediatric Neurosurgery)

2. Barlow P: Indications for endoscopic third ventriculostomy: a review of successful and failed cases. **British Journal of Neurosurgery** **11**:456, 1998

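### Study participation ends at shunt/ETV failure although scans are scheduled for every patient, so the t-test on ventricular size has no common time point and mixes scans at recurrence with routine scans

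*Protocol*

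**What the plan says.** Four parts of the Protocol bear on this point.

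- Study procedure, follow-up: "Follow-up will be arranged for 6 weeks, 6 months and one year for all study patients", and "At the 6 week and 6 month clinic the patient will have a cranial imaging to assess ventricular size". No scan is scheduled at one year.
- Study procedure, exit: there are three ways out of the study, and the first is "The patient represents with shunt/ETV failure". A final form is completed at exit.
- Data recording and proformas: besides the admission and discharge record there is one further form, "Follow-up proforma to be filled in at one year or earlier if treatment fails". Its template has one visit date, one CT field and one MRI field, and no date for either scan.
- Statistical considerations: "Mean numbers of reattendances and mean reduction in ventricular size will be compared using student's t-test". No time point is given. Ventricular size change is the second of the secondary endpoints, which the endpoints section says are assessed in every patient.

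**The concern.** A patient who fails before a scheduled scan cannot both be scanned on schedule as a study patient and have left the study. The event that removes the patient is the primary outcome, and it may be established radiologically, so leaving is tied to ventricular size itself. It is also expected to happen more often in one arm.

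At stake is what the comparison of ventricular size means. If the form completed at exit is the data source, a failed patient's value describes recurrent hydrocephalus and a well patient's value describes routine follow-up at another time. The difference between arms then partly restates the difference in failure rates. This would remain even if size were measured perfectly. A later analysis plan could choose among the scans that exist, but it could not recover scheduled scans that were never recorded because the patient had left.

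**Working it through.** **Inputs**

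- Failure after shunt revision: "In 47 of those cases (43.5%), a further procedure was needed because of complications with the new shunt", of 108 revisions. 47/108 = 43.5%, so the Protocol's figure reproduces; one-year success is 56.5%.
- Failure after ETV: "There are series which show higher success rates (70%) with ETV following shunt failure", taken as 30% failure. The series are retrospective, and the figure is not stated to be a one-year rate.
- 100 patients per arm (Randomisation process).
- Timing of failures within the year: not given.

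**Step 1. What each kind of patient contributes under the text**

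| Patient | Scheduled scans while in the study | Follow-up form completed |
|---|---|---|
| Fails before 6 weeks | none | at failure |
| Fails between 6 weeks and 6 months | 6 weeks only | at failure |
| Fails between 6 and 12 months | 6 weeks and 6 months | at failure |
| No failure | 6 weeks and 6 months | at one year |

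The form does not say which scan its CT and MRI fields describe.

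**Step 2. Ceiling: forms completed at failure**

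43.5 + 30 = 73.5 of 200 patients, or 36.75%. The gap between arms is 43.5 − 30 = 13.5 percentage points.

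**Step 3. Failures before a scheduled scan**

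An assumed curve is needed: F(t) = 1 − S^(t^k), with t in years, S the one-year success rate, k = 1 for a constant hazard and smaller k for earlier failure. For example, at 6 months with k = 1: shunt 1 − 0.565^0.5 = 24.8%; ETV 1 − 0.70^0.5 = 16.3%.

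| k (assumed) | Before 6 weeks: shunt / ETV / pooled | Before 6 months: shunt / ETV / pooled |
|---|---|---|
| 1 | 6.4% / 4.0% / 5.2% | 24.8% / 16.3% / 20.6% |
| 0.7 | 11.8% / 7.6% / 9.7% | 29.6% / 19.7% / 24.7% |
| 0.5 | 17.6% / 11.4% / 14.5% | 33.2% / 22.3% / 27.8% |
| 0.3 | 25.8% / 17.0% / 21.4% | 37.1% / 25.2% / 31.1% |

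The gap between arms is about 2 to 9 points at 6 weeks and 8.5 to 12 points at 6 months.

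**Step 4. What mixing could do to the t-test**

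Suppose that well patients show the same mean reduction in both arms, that every failure contributes its scan at recurrence, and that this scan shows g standard deviations less reduction. The difference between arms is (0.435 − 0.30) × g = 0.135g in favour of ETV. Its standard error is √{[(1 + 0.21g²) + (1 + 0.246g²)]/100}, where 0.21 = 0.30 × 0.70 and 0.246 = 0.435 × 0.565.

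- g = 1: 0.135 SD, standard error 0.157, ratio 0.9.
- g = 2: 0.27 SD, standard error 0.196, ratio 1.4.

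The Protocol gives no value for g; 1 to 2 is an assumption to show scale.

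**The case against.** The best reply is that the text is coherent: visits are arranged for patients in the study, and a patient who fails is no longer in it. Stopping at first failure suits the primary endpoint and the Kaplan-Meier analysis, and a scan after failure would reflect a second operation. This stands for the primary endpoint. It does not stand for ventricular size, which is to be assessed in every patient and compared as a mean at no named time.

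Three stronger readings are tempting, and the document does not support them.

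- A reader might infer that 37% of patients have no ventricular measurement. That figure is the one-year failure rate. Patients who fail after 6 months have had both scheduled scans, and those who fail after 6 weeks have had the first. Suspected failures are investigated in the usual way, cranial CT is described as routine in suspected malfunction, and the form completed at failure has imaging fields. Mistiming is better supported than absence.
- A reader might infer that the analysis will be confined to patients who did not fail. No section prescribes that.
- A reader might fault the lack of a scoring rule for failed patients. That is commonly left to the statistical analysis plan, which is not shown, so its absence is no finding. The exit rule is different, because it decides which data are collected.

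It is also fair to say that the imbalance between arms rests on one unit's audit and retrospective ETV series.

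**Conclusion.** The point holds for one secondary endpoint. The exit rule does not fit with scheduled imaging for every patient, and with a single undated form it leaves the t-test on ventricular size comparing scans at recurrence with routine scans, in proportions expected to differ by arm.

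Up to about 37% of forms could be completed at failure, and this is a ceiling. The share failing before a scheduled scan is about 5-21% at 6 weeks and 21-31% at 6 months, and these figures depend on the assumed timing curves. If all failures contribute their exit scan, the spurious difference could be about 0.9 to 1.4 standard errors in favour of ETV. That is enough to colour the result, though not by itself to reach significance, and it rests on the assumed gap of 1-2 SD. The primary endpoint is not affected by this point: a patient who needs further surgery within the year is correctly counted as a failure.

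**What to change.** - **Study procedure.** State that failure ends assessment of the primary endpoint but not study follow-up, so that the scheduled visits and scans continue to be recorded for all randomised patients.
- **Secondary endpoints, Data recording and proformas, Statistical considerations.** Name one time point for ventricular size and record the date of each scan. The 6-week scan is one candidate: it is scheduled in both arms, and fewer patients will have failed by then. It also avoids the disagreement between the 6-month visit in Study procedure and the 3-month visit named under Secondary endpoints.
- **Comparison.** Compare all randomised patients at that time point. Report scans taken at failure separately and do not mix them in.

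The cost is small. The Protocol describes these visits as no different from normal follow-up after treatment of a blocked shunt, so the main extra work is keeping study records after failure. The downside is that some patients' scans will reflect a second operation; the comparison is then of the randomised strategies, and the report should say so.

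An analysis giving failed patients the worst rank could serve as a sensitivity analysis but is not required. It builds the failure rate into the endpoint: at 30 against 43.5 failures per 100, with well patients alike in both arms, the rank test would give z of about 1.7 from the failures alone.

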- The procedure will be deemed a failure if the patient requires further surgical intervention within a year for treatment of their hydrocephalus. We felt that one-year follow-up was appropriate as most shunt and ETV failures occur in the first year following the procedure^{9,12}. The need for further surgery will be determined clinically or radiologically. In the case of patients who are in the ETV arm of the study, a sagittal MRI demonstrating the third ventricle floor will be sought where possible.

Secondary endpoints:

1. Occurrence of complications from surgery
2. Ventricular size changes
3. Length of inpatient stay
4. Number of re-attendances (excluding scheduled ones at 6 weeks, 3 months and 1 year) with symptoms related to their hydrocephalus/wound or implant.

Safety

Where either treatment would be deemed unsafe, the patient would be excluded from the study.

The risks of surgery are:

1. Death (less than 1% for shunt and ETV)
2. Epilepsy (approximately 5% short term risk in both treatments)
3. Minor vascular injury – Both treatments involve the passage of instruments through the brain to the ventricle. The risk of bleeding from this is about 5%. Most bleeds are sub clinical and don't result in neurological deficit. The risk of a bleed causing a deficit is about 1-2% for both treatments
4. Major vascular injury: This is a risk with ETV where basilar artery injury has occurred - death from it has been reported¹. However, most large series of patients treated with ETV, report no such injuries.
5. Infection: The shunt infection rate in this unit at present is 5%. The rate of CSF infection or ventriculitis is 0-10% in large series^{8,11,21} The rate of infection
6. CSF wound leak: This occurs in up to 5% of newly implanted shunt and is a high risk factor for infection. In the case of ETV it usually means that the ETV will not work and a shunt is needed²¹
7. Overdrainage and slit ventricle syndrome. This is a rare but serious problem in children treated with shunts. It can cause severe headaches and often requires further shunt surgery. It is not a recognised complication of ETV²²
8. Subdural haematomas. This is a complication seen with overdrainage of shunts in adults. It can mean that a patient will require surgery to remove the haematomas and shunt revision. It is also rarely seen with ETVs.

Subject withdrawal

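### Secondary endpoint 4 (re-attendances) rests on two conflicting visit lists, cannot be extracted from the follow-up form, and is compared over follow-up that ends at failure, with a bias of undetermined direction

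*Protocol*

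**What the plan says.** Four parts of the protocol bear on this endpoint.

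- **Definition** (Secondary endpoints, item 4): "Number of re-attendances (excluding scheduled ones at 6 weeks, 3 months and 1 year) with symptoms related to their hydrocephalus/wound or implant".
- **Visit plan and exit** (Study procedure): "Follow-up will be arranged for 6 weeks, 6 months and one year for all study patients". The next sentence relies on the same schedule: "At the 6 week and 6 month clinic the patient will have a cranial imaging to assess ventricular size". The first of three listed ways to leave the study is "The patient represents with shunt/ETV failure", and "A final proforma will be filled in at the patient's exit from the study". The same section describes unscheduled presentation with symptoms as a route by which failure is investigated and confirmed.
- **Data capture** (Data recording and proformas, and the follow-up form): "Follow-up proforma to be filled in at one year or earlier if treatment fails". The only count on that form is "Number of visits post discharge".
- **Analysis** (Statistical considerations): "Mean numbers of reattendances" are to be compared between arms by Student's t-test. No allowance for differing follow-up time is stated.

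**The concern.** There are three separate weaknesses, and only the first is a contradiction in the text.

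1. **Visit lists.** The endpoint removes a 3-month visit that Study procedure does not plan, and does not remove the 6-month visit that it does plan.
2. **Form.** The endpoint needs attendances that were both unscheduled and symptomatic. The form gives one undivided total. A statistical analysis plan could not repair this, because it cannot recover information that was never collected.
3. **Follow-up time.** If the form is closed at failure, a patient who fails early has little time to accumulate attendances. Failure is also the primary endpoint, so time at risk is itself an outcome of treatment. A difference in mean counts could then appear when the underlying re-attendance rates are equal, or a true difference could be hidden.

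At stake is the interpretation of one secondary endpoint. The primary chi-squared comparison is not affected.

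**Working it through.** **Visit lists side by side**

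| Source | Early | Middle | Late |
|---|---|---|---|
| Study procedure | 6 weeks | 6 months | one year |
| Secondary endpoints, item 4 | 6 weeks | 3 months | 1 year |

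The lists agree on two visits and differ on one. Because the endpoint is restricted to attendances with related symptoms, a routine 6-month visit by a well patient does not qualify. Only patients who are symptomatic at that clinic are affected.

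**Inputs for the follow-up question**

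- One-year failure after shunt revision: 47/108 = 43.5% (protocol background), which reproduces the stated percentage.
- One-year failure after ETV: 100% − 70% = 30%, from the retrospective success rate quoted in the background.
- Background re-attendance rate r per patient-year: not given. Assumed equal in both arms and varied.
- Timing of failure: not given. Assumed exponential, or front-loaded (Weibull shape 0.5 or 0.3).

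The protocol gives no rate, standard deviation or target difference for this endpoint, so there is no planned figure to reproduce.

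**Step 1: mean observed time.** With one-year failure f, let λ = −ln(1 − f) and S(t) = exp(−λt^k). Mean time to failure or one year is the integral of S(t) from 0 to 1. For k = 1 this is f/λ: 0.435/0.571 = 0.762 years and 0.30/0.357 = 0.841 years.

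| Timing of failure | 43.5% arm (years) | 30% arm (years) | Ratio |
|---|---|---|---|
| Exponential | 0.762 | 0.841 | 0.906 |
| Shape 0.5 | 0.690 | 0.791 | 0.872 |
| Shape 0.3 | 0.648 | 0.762 | 0.851 |

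Observed time is therefore about 9% to 15% shorter in the arm with more failures.

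**Step 2: expected mean count.** If the failure presentation is not counted, the mean is r × observed time. If every failure adds one counted attendance, the mean is f + r × observed time. With exponential timing:

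| r per year | Not counted: 43.5% arm vs 30% arm | Difference | Counted: 43.5% arm vs 30% arm | Difference |
|---|---|---|---|---|
| 0.25 | 0.190 vs 0.210 | −0.020 | 0.625 vs 0.510 | +0.115 |
| 1 | 0.762 vs 0.841 | −0.079 | 1.197 vs 1.141 | +0.056 |
| 2 | 1.524 vs 1.682 | −0.158 | 1.959 vs 1.982 | −0.023 |

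**Step 3: where the sign changes.** With the failure presentation counted, the arms are equal when r = (0.435 − 0.30)/(difference in observed time). This gives 1.70 (exponential), 1.33 (shape 0.5) and 1.19 (shape 0.3) per patient-year. A simpler assumption, all failures at 2 months, agrees. Observed time is (0.565 × 12 + 0.435 × 2)/12 = 0.6375 years against (0.70 × 12 + 0.30 × 2)/12 = 0.75 years, and the crossover is 0.135/0.1125 = 1.2.

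**Step 4: would a rate per time observed be enough?** Only if the failure presentation is left out. With it counted and failure at 2 months, the rates are 0.435/0.6375 + r = 0.68 + r and 0.30/0.75 + r = 0.40 + r. The difference then largely restates the primary endpoint. With it left out, both arms return r.

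**The case against.** The strongest reply is that the endpoint's intent is clear. The definition says scheduled visits are excluded, so a sensible analyst would exclude whatever clinics were actually planned. The symptom restriction limits the damage further, the endpoint is the last of four secondary ones with no stated power, and preferring a count model to a t-test with about 100 patients per arm is partly a matter of taste. Much of this stands. The visit-list slip alone would be minor, and the t-test as such is not the problem. It does not answer the other two points: the form cannot show which visits were unscheduled or symptomatic, and no choice of test removes unequal follow-up that depends on outcome.

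Two stronger readings are tempting, and the protocol supports neither.

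- A reader might infer that ending the count at failure must flatter the arm with more failures. That would follow if failures added nothing to the count. But a failure that comes to light through an unscheduled symptomatic presentation is itself such an attendance, and nothing in the protocol excludes it. This pushes the other way and can outweigh the lost time. The inference would be better founded if the form's undivided total were analysed in place of the endpoint. With exponential timing, scheduled visits would average 2.25 and 2.50, a difference of −0.24 before rounding, and adding 0.135 for failure presentations still leaves −0.11. That total is not the endpoint the protocol defines.
- A reader might infer that the 6-month clinic adds about one visit for every patient still in the study. The symptom restriction rules that out.

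**Conclusion.** The point holds in a limited form. The two visit lists contradict each other and must be reconciled. The form cannot yield the endpoint as defined. The comparison of raw means is confounded with the primary outcome, because counting ends at failure.

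Under the assumed failure of 43.5% and 30%, the arm with more failures is observed for about 9% to 15% less time. The 15% is the extreme of the timings tried, not a central estimate. The direction of bias is undetermined. If the failure presentation is not counted, the arm with more failures looks better. If it is counted, that arm looks worse below roughly 1.2 to 1.7 re-attendances per patient-year and better above. These crossovers assume equal background rates and one counted attendance for every failure. If some failures are found at planned clinics, the crossover falls in proportion. The protocol gives neither the background rate nor the status of the failure presentation.

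This deserves correction because the endpoint is named and the repair is cheap, but it does not threaten the primary analysis.

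**What to change.** 1. Reconcile the two visit lists. Wording the exclusion as attendances other than protocol-scheduled visits, with the schedule stated once, avoids a second list.
2. Replace the single visit total on the follow-up form with a dated entry for each unscheduled attendance and its reason.
3. State whether the presentation at which failure is found counts as a re-attendance.
4. Count attendances to one year in all patients regardless of failure, so that both arms are compared over the same period.
5. If counting must stop at failure, leave the failure presentation out and compare rates per time observed, using a count model (for example negative binomial) with log follow-up time as offset.

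The cost is one corrected line, one changed form field and some extra record-keeping after failure. The primary endpoint and the sample size do not change.
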